12.3 Sample Size and Accrual Rate

The minimum study accrual will be 4 patients, when both dose levels are found to be not tolerable during the safety lead-in portion. The expected total sample size for the study is 40 evaluable patients, assuming that dose level 1 (starting dose level) is safe and passes the first stage response evaluation in Phase 2, and safety lead-in patients are also evaluable for response. However if dose level 1 is not tolerable and dose level -1 is tolerable, the study will need to accrue up to 48 evaluable patients for the safety lead-in and phase 2 evaluations. Accounting for up to 10% inevaluable patients for unacceptable toxicity evaluation during Safety lead-in or inevaluable for response during Phase 2, the maximum accrual for the study is estimated to be 53 patients. Given that this is a multicenter study including high-volume DLBCL centers, we anticipate completing study accrual within 24 months.

12.4 Monitoring for Stem Cell Mobilization Failure and Non-relapse Mortality after ASCT

The rate for failure to collect adequate CD34 stem cells (after 2 attempts) for autologous transplantation will be monitored in patients who proceed to stem cell collection (regardless of the dose level of PolaR-

ICE they were enrolled on). Routine collection failure rate for RICE would be around 15%. A Bayesian rule will be used for this monitoring. The prior distribution of the failure rate is assumed to be Beta (0.15, 0.85) with a mean of 15%. If based on the observed collection failure data, the posterior probability of the failure rate being greater than 15% is 90% or higher, the stopping rule will be triggered. Operationally, the rule will be triggered if at least 3/5, 4/10, 6/20, 8/30, or 10/40 patients fail to mobilize adequate CD34 cells within 2 attempts.

The incidence of non-relapse mortality in the first 100 days after ASCT will also be monitored among patients who went to ASCT, regardless of the dose level of PolaR-ICE they were enrolled on. A second case of such death within 100 days following ASCT will trigger a stopping rule.

If either monitoring rule is triggered, the study accrual will be halted. A full review of the study data will be undertaken by the study team, and the results will be submitted to the DSMC. The study team may propose to modify the study if deemed necessary. The DSMC will also perform their independent assessment of these events. The study accrual will not be resumed without approval from the DSMC.

12.5 Toxicity monitoring for post-HCT Pola

To assess the safety of Pola consolidation in the post-HCT setting, we will monitor the number of patients experiencing severe toxicities during post-HCT Pola consolidation, defined as any of the following AEs that is **at least possibly** attributed to Pola or to PolaR-ICE:

- Grade 3 peripheral neuropathy that does not resolve to grade 2 or better within 7 days
- Any Grade 4 AE with the exception of:
 - Grade 4 neutropenia (despite the use of growth factor) or grade 4 thrombocytopenia that lasts ≤ 21 days
 - Grade 4 laboratory abnormalities that resolve to Grade ≤ 2 within 10 days
 - Grade 4 metabolic laboratory abnormalities that are not clinically significant
- Any Grade 5 AE

The City of Hope Data Safety Monitoring Committee (DSMC) will review the toxicity data on this study every 6 months. The stopping rule for "severe" toxicities will start when there are at least 6 patients on the study who received post-HCT Pola (regardless of the dose level of PolaR-ICE they received or whether they were enrolled in the safety lead-in or Phase 2 portion of the study). If during such review, the proportion of patients having any of the severe toxicities is 33% or higher, the study accrual will be halted. A full review of the study data will be undertaken by the study team, and the results will be submitted to the DSMC. The study team may propose to modify the study if deemed necessary. The DSMC will also perform their independent assessment of these events. The study accrual will not be resumed without approval from the DSMC.

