12.1.1 Safety Lead-in

Prior to formally initiating the Phase 2 response assessment, a patient safety lead-in portion will be conducted to ensure there are no unexpected toxicities with PolaR-ICE salvage therapy. The decision to open to Phase 2 will primarily be based on the number of safety lead-in patients experiencing unacceptable toxicities during the first 2 cycles of PolaR-ICE salvage, but will also take into consideration other data available at the time of decision making, including toxicities observed in cycle 3, the ability to

proceed to transplant after PolaR-ICE and delays due to study treatment-related toxicity between PolaR-ICE and transplant. The unacceptability toxicities are defined in Section 11.2. Patients evaluable for unacceptable toxicities during the Safety Lead-in are defined in Section 12.2.

During the safety lead-in portion of the study, a design that is slightly modified from the IQ rolling 6 design will be used.[7] In this design, up to 8 evaluable patients may be treated at each dose level, and the highest dose level with <33% evaluable patients having unacceptable toxicities will be considered tolerable with respect to unacceptable toxicities. Given the expected safety profile of PolaR-ICE, we adopt this design which may allow up to 6 patients at risk at any time instead of some other designs which allow up to 3 at risk. The rules of the proposed design are outlined below.

- 1) When there is no patient with unacceptable toxicities, accrual can continue for up to 8 patients with up to 6 patients at risk (i.e., under unacceptable toxicity observation) at the same time.
- 2) If there is no DLT in 5+ evaluable patients with no others at risk, (i.e., 0/5, 0/6, 0/7, or 0/8), the current dose level will be considered tolerable.
- 3) After 1 patient with unacceptable toxicity is reported, accrual can continue to up to 6 patients (i.e. <6 at risk); to accrue the 7th or the 8th patient, there must be ≤3 patients at-risk.
- 4) If there is 1 patient with unacceptable toxicity in 6-8 evaluable patients with no others at risk (i.e., 1/6, 1/7, or 1/8), the current dose level will be considered tolerable.
- 5) If there are 2 patients with unacceptable toxicities when ≤6 patients are treated, the current dose level will be considered intolerable (and dose de-escalated if at dose level 1).

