12.1.2 Phase 2 design

The Phase 2 portion of the study adopts a two-stage design. Patients who were enrolled during the safety lead-in portion at the final dose level deemed tolerable for Phase 2 will also be included in the Phase 2 response evaluation if they are evaluable for response.

At the first stage, 20 patients will be enrolled. If <8 complete responses are seen, the accrual will be terminated. If at least 8 patients achieve a complete response, the trial will continue to the second stage. At the second stage, 20 additional patients will be entered. At the end of stage 2, if 21 or more patients out of the total 40 patients experience a complete response, the combination will be considered worthy of further study. If <21 patients experience a complete response then no further investigation of the combination is warranted.

The 2-stage design aims to differentiate between the null hypothesis (disappointing rate) of 40% CR rate and an alternative hypothesis (promising rate) of 60% CR rate. The null hypothesis of 40% CR rate is based on a large randomized study comparing R-ICE with R-DHAP (rituximab, dexamethasone, cytarabine, cisplatin) as salvage regimen followed by ASCT for relapsed/refractory DLBCL.[8] Similar complete

response rates were observed after 3 cycles of R-ICE (37%, n=197) vs. 3 cycles R-DHAP (40%, n=191). Therefore, we would consider a 40% CR rate a discouraging rate and 60% a promising CR rate for this regimen to merit further study. The design has a 1-sided type I error of 7.3% and a power of 87%. The expected sample size under the null hypothesis is 31.7, and the design has a 42% chance of early termination after Stage I if the true CR rate is 40%.

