12.2 Evaluable Participants and Participant Replacement

- Evaluable for toxicity: Patients who receive at least one dose of protocol therapy are evaluable for toxicity.
- Evaluable for unacceptable toxicity during Safety Lead-in: Patients evaluable for unacceptable toxicity (defined in Section 11.2) are:
 - 1) Those who receive the full dose of Pola, the full doses of rituximab and carboplatin, and at least 67% of the doses of etoposide and ifosfamide during the first 2 cycles of Salvage, OR
 - 2) Those who experience any unacceptable toxicity during the first 2 cycles of Salvage regardless of actual dose of protocol therapy received.

During safety lead-in, patients who are not evaluable for unacceptable toxicities will be replaced.

• Evaluable for response during Phase 2:

Evaluable patients are defined as eligible participants who have received at least one cycle of PolaR-ICE salvage therapy and have at least one disease evaluation post-baseline.

Patients will be evaluable and be considered non-CR in the primary response evaluation if they discontinued study therapy prior to having a response assessment after 2 cycles of PolaR-ICE because of progressive disease or unacceptable toxicity (rather than due to withdrawal of consent or investigator decision). If a patient discontinues study treatment prior to the first response assessment after 2 cycles of PolaR-ICE due to progressive disease, the treating physician is encouraged to obtain imaging to confirm progression.

During Phase 2 enrollment, participants who are not evaluable for response will be replaced and excluded from Phase 2 efficacy analyses, but will be included in the general toxicity analyses if they receive any protocol treatment.

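### Once the lead-in clears a dose, no pre-stated numeric rule pauses accrual for unacceptable toxicity during PolaR-ICE salvage in Phase 2

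*Combined protocol and SAP*

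**What the plan says.** Section 12.1.1 limits the salvage rule to the lead-in: "During the safety lead-in portion of the study, a design that is slightly modified from the IQ rolling 6 design will be used". A dose clears at 0/5 to 0/8, 1/6 to 1/8, 2/7 or 2/8 evaluable patients with unacceptable toxicity (defined in Section 11.2 over the first 2 cycles). The step to Phase 2 is not the count alone: "The decision to open to Phase 2 will primarily be based on the number of safety lead-in patients experiencing unacceptable toxicities", with cycle 3 toxicity, ability to reach transplant and treatment-related delays also weighed. The evaluability definition in Section 12.2 has the same limit: "Evaluable for unacceptable toxicity during Safety Lead-in".

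The numeric halts that operate after that are:
- Section 12.1.2, after 20 patients: "If <8 complete responses are seen, the accrual will be terminated".
- Section 12.4, collection failure among patients who go to collection (3/5, 4/10, 6/20, 8/30, 10/40).
- Section 12.4, non-relapse deaths after ASCT: "A second case of such death within 100 days following ASCT will trigger a stopping rule".
- Section 12.5, severe toxicity in 33% or more once at least 6 patients have received post-HCT Pola: "we will monitor the number of patients experiencing severe toxicities during post-HCT Pola consolidation".

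Oversight without a threshold continues. Section 12.5 says the DSMC "will review the toxicity data on this study every 6 months". Section 14.6 requires expedited reporting of all SAEs during treatment, Section 16.3 has the PMT consider whether enrolment should go on, and Section 16.6 sends PMT progress reports to the DSMC.

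**The concern.** PolaR-ICE is the investigational part of the regimen that every patient receives, yet its numeric tolerability check ends after 5-8 evaluable patients. The plan pre-states a 33% pause for post-HCT Pola, which only some patients reach, and has no counterpart for salvage. The collection, post-ASCT death and consolidation rules see only patients who get that far. A patient lost to toxicity in cycles 1-2, fatal events included, enters none of those three populations. If salvage proves more toxic than the lead-in suggested, the level at which accrual pauses would be chosen after the data are seen.

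**Working it through.** **1. The plan's own figures.** Stop if 7 or fewer CRs in 20; succeed if 21 or more in 40. At a CR rate of 40%: P(X ≤ 7 | 20) = 0.416, type I error 0.073, expected size 20 + 20 × (1 − 0.416) = 31.7. At 60%: power 0.866. All match Section 12.1.2. The collection boundaries in Section 12.4 also reproduce: each is the smallest count with posterior probability of at least 0.90 under the Beta(0.15, 0.85) prior.

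**2. Patients outside any numeric salvage rule.** Lead-in patients at the cleared dose count toward the 40 if response-evaluable. Then 40 − 8 = 32 to 40 − 5 = 35 remain, or 20 − 8 = 12 to 20 − 5 = 15 if Stage 1 stops the trial. At a true 33% rate, 0.33 × 32 = 10.6 to 0.33 × 35 = 11.6 of the 32-35 would be expected to have an event.

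**3. How often the count rule clears a dose with true rate p.** The answer depends on how patients enter, so three patterns bracket it.
- A, one at a time (clears at 0/5 or 1/6): (1−p)^5 + 5p(1−p)^5. At p = 0.33: 0.135 + 0.223 = 0.358.
- B, eight treated, with 2 or more in the first 6 intolerable: P(at most 1 of the first 6 and at most 2 of 8).
- C, second events surface only after 7-8 are treated: P(at most 2 of 8).

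| True rate | A | B | C |
|---|---|---|---|
| 33% | 0.358 | 0.329 | 0.476 |
| 40% | 0.233 | 0.203 | 0.315 |

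One-sided 95% upper limits (Clopper-Pearson) on the rate are 45% after 0/5, 58% after 1/6, 66% after 2/7 and 60% after 2/8.

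**4. What a pre-stated pause would do.** Carry the lead-in counts forward and apply the 33% threshold at 10, 20 and 30 patients: 0.33 × 10 = 3.3, so 4; 0.33 × 20 = 6.6, so 7; 0.33 × 30 = 9.9, so 10. An exact binomial recursion gives the pause probability given clearance. For comparison, the last column checks at every patient from the 10th to the 40th.

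| True rate | Three looks: A | B | C | Every patient: range A-C |
|---|---|---|---|---|
| 15% | 0.014 | 0.011 | 0.016 | 0.038-0.055 |
| 20% | 0.055 | 0.045 | 0.061 | 0.113-0.148 |
| 25% | 0.150 | 0.130 | 0.161 | 0.250-0.301 |
| 30% | 0.307 | 0.276 | 0.320 | 0.441-0.498 |
| 33% | 0.422 | 0.387 | 0.434 | 0.566-0.619 |
| 40% | 0.690 | 0.655 | 0.696 | 0.814-0.845 |
| 50% | 0.928 | 0.912 | 0.927 | 0.974-0.980 |

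The three-look figures assume that at least 30 patients are treated and that no other halt intervenes.

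**5. Lag.** With 40 patients over 24 months (about 730 days) and a 42-day window, 40 × 42 / 730 = 2.3 patients are still under observation at any look; at the maximum accrual of 53 it is 3.0. Some Section 11.2 events, such as Grade 4 cytopenia lasting more than 21 days, can take longer than 42 days to establish.

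**The case against.** The strongest reply is that this is a design choice and not an error. The plan contradicts nothing, puts its count rule where the dose decision is made, and then relies on people: non-COH sites report qualifying SAEs within 24 hours (Section 14.6.2.1), the PMT considers further enrolment, and the DSMC reviews toxicity. That stands. A reader might infer that salvage toxicity in Phase 2 goes unmonitored or cannot halt the trial; the documents do not support that. Section 16.6 also refers to an institutional DSMP that is not in the documents and may add to this oversight.

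A reader might also infer that tolerability is settled by 5-8 patients alone. Section 12.1.1 weighs other data too, so the clearance probabilities describe the count rule and not the whole decision.

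The response rule reacts to toxicity in part: "Patients will be evaluable and be considered non-CR in the primary response evaluation if they discontinued study therapy prior to having a response assessment" because of progression or unacceptable toxicity. But it looks once, at 20 patients, and a patient who has an unacceptable toxicity, continues and reaches CR counts as a success.

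Finally, a numeric rule has false alarms. Checking after every patient would pause 44-50% of trials at a true 30%, below the plan's own limit. That is a fair argument against continuous checking, and the reason to prefer a few fixed looks.

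**Conclusion.** The gap is real and limited. After the lead-in, this protocol pre-states no count of salvage toxicity that pauses accrual; a halt depends on judgement. The number affected (32-35, or 12-15) is conditional on response-evaluability of the lead-in patients and on the Stage 1 outcome. The chance that the count rule passes a dose at or above the plan's own limit is material: 33-48% at a true 33% and 20-32% at 40%, taking independent patients and the three entry patterns as the range. These figures do not show that PolaR-ICE is too toxic; the true rate is unknown. The change is worth making because it extends safeguards the plan already uses elsewhere.

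**What to change.** In Section 12, add an accrual pause for salvage toxicity in Phase 2 that uses the Section 11.2 definition, the plan's 33% threshold and the Section 12.4-12.5 procedure: halt, study-team review, restart only with DSMC approval. Apply it at a few fixed looks, for example when 10, 20 and 30 patients treated at the Phase 2 dose, lead-in included, have completed the 2-cycle observation window, pausing at 4/10, 7/20 or 10/30 or more. State in Section 12.2 that the denominator is all patients treated at that dose, which differs from the lead-in evaluable set, and that after an approved restart the rule is next applied at the following look. Report the operating characteristics given clearance: about 1-2% at a true 15%, 5-6% at 20%, 13-16% at 25%, 28-32% at 30%, 39-43% at 33%, 66-70% at 40% and 91-93% at 50%. The sponsor may choose another schedule if its characteristics are stated. Describe it as a pause for review, not a termination or mortality rule, covering cycles 1-2 only.

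The cost is a paragraph in Section 12, a line or two in Section 12.2, and per-patient adjudication of Section 11.2 events in Phase 2. Section 14.5 already collects all Grade 2 or higher AEs in Cycles 1 and 2, and Table 13.3 makes Phase 2 forms due within 10 days. The downsides are some review pauses at true rates below 33%, lower detection than continuous checking (which reaches 57-62% at 33% and 81-85% at 40%), and a lag of about 2-3 patients.

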11.2 Primary Endpoint(s)

Unacceptable Toxicity: defined as any of the following events occurring during the first 2 cycles of treatment that is at least possibly related to study treatment:

- Any Grade 3 or higher non-hematologic toxicity that does not resolve to Grade 1 or better within 7 days with the exception of:
 - Grade 3 asymptomatic laboratory abnormalities, including lipase or amylase, that are not clinically relevant, not requiring hospitalization or delay of treatment
 - Grade 4 isolated electrolyte abnormalities that are not clinically significant including, but not limited to, hypo-or hyperglycemia, hypo-or hypernatremia, hypo-or hyperkalemia, hypo-or hypermagnesemia, or hypo-or hypophosphatemia, that resolve, with or without intervention, to Grade 2 in less than 72 hours
 - Grade 3 nausea, vomiting, or fatigue controlled with supportive measures (and does not require hospitalization, TPN, or tube feeding)
 - Grade 3 infusion reaction that resolves with appropriate management to Grade 1 or better within 24 hours
 - Alopecia of any grade
- Any Grade 3 or 4 thrombocytopenia associated with clinically significant bleeding.
- Any Grade 4 neutropenia (despite the use of growth factor) or grade 4 thrombocytopenia (without clinically significant bleeding) that lasts > 21 days.
- Any Grade 4 anemia unexplained by underlying disease.
- Any treatment-related toxicity that delays cycle 2 treatment for >2 weeks.
- Any Grade 5 toxicity.

Complete response (CR) rate: defined as the proportion of response-evaluable participants (see Section 12.2) that achieve a CR after 2 cycles of PolaR-ICE therapy.

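### Section 12.5 exempts Grade 4 thrombocytopenia of up to 21 days from the post-transplant severe-toxicity count without the bleeding condition that Section 11.2 puts on the same allowance

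*Combined protocol and SAP*

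**What the plan says.** Section 12.5 defines the severe toxicities monitored during Pola consolidation. They must be at least possibly attributed to Pola or PolaR-ICE, and there are three limbs:

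- One Grade 3 event: "Grade 3 peripheral neuropathy that does not resolve to grade 2 or better within 7 days".
- "Any Grade 4 AE with the exception of" a short list. The list includes "Grade 4 neutropenia (despite the use of growth factor) or grade 4 thrombocytopenia that lasts ≤ 21 days" and "Grade 4 laboratory abnormalities that resolve to Grade ≤ 2 within 10 days". Neither of these mentions bleeding.
- Every Grade 5 event.

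The rule starts once at least 6 patients have received post-transplant Pola. The DSMC reviews the toxicity data every 6 months, and accrual halts if the proportion with a severe toxicity is 33% or higher.

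Section 11.2 defines unacceptable toxicity for the safety lead-in, "defined as any of the following events occurring during the first 2 cycles of treatment". It treats thrombocytopenia in two linked limbs. The first is "Any Grade 3 or 4 thrombocytopenia associated with clinically significant bleeding", with no limit on duration. The second is "Any Grade 4 neutropenia (despite the use of growth factor) or grade 4 thrombocytopenia (without clinically significant bleeding) that lasts > 21 days".

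**The concern.** The two sections use nearly the same construction for cytopenias: the same growth-factor parenthesis and the same 21-day limit. Section 11.2 reserves the 21-day allowance for thrombocytopenia without clinically significant bleeding and counts the bleeding cases separately. Section 12.5 keeps the allowance but has neither the qualifier nor the bleeding limb, and gives no reason.

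The numerator of the 33% rule is at stake. Any patient whose only relevant event is short Grade 4 thrombocytopenia with clinically significant bleeding below Grade 4 enters the denominator and not the numerator. Each such patient lowers the monitored proportion and makes a halt less likely. The documents themselves make thrombocytopenia foreseeable: Table 6.2 reports it in 49% of patients on Pola with bendamustine and rituximab, against 33% without Pola. The toxicity of Pola consolidation is also a stated secondary objective.

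**Working it through.** **Step 1. Classify the same event under both definitions** (related thrombocytopenia with clinically significant bleeding).

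| Event | Section 11.2 (salvage cycles 1–2) | Section 12.5 (consolidation) |
|---|---|---|
| Grade 4 platelets, 21 days or less, bleed Grade 3 or lower | Counts | Not counted: 21-day exception |
| Grade 4 platelets, more than 21 days, bleed Grade 3 or lower | Counts | Counts, unless another exception is read to apply |
| Grade 3 platelets, bleed Grade 3 or lower | Counts | Not counted: no Grade 3 event but neuropathy is listed |
| Any platelet grade, attributed bleed of Grade 4 or 5 | Counts | Counts: the bleed is its own event and is not an exception |

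The first row is the gap that the exception creates. The third has a different cause, the Grade 4 basis of Section 12.5. If a platelet count is read as a laboratory abnormality, the 10-day exception also covers first-row cases that recover quickly. Amending the 21-day exception alone would then not close the gap.

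**Step 2. The plan's threshold as counts.** The plan states 33% and a minimum of 6 patients. It gives no error rate, power or expected event rate for this rule, so there is no operating characteristic to reproduce. The smallest k with k/n ≥ 0.33 is 2/6, 4/10, 4/12, 6/18, 7/20 and 8/24.

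**Step 3. Illustrative effect.** Assumptions, none from the documents:

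- A share q = 15% of patients has a toxicity that counts today.
- A further share b has only the uncounted event.
- Patients are independent.
- Looks fall at fixed patient numbers.

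The halt probability is the chance that the cumulative count reaches the threshold at any look. It is computed exactly from the binomial at rate q as written, and at q + b if the event is counted.

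First look at n = 6, q = 0.15: 1 − 0.85^6 − 6(0.15)(0.85^5) = 1 − 0.377 − 0.399 = 0.224. Carrying the paths that have not halted forward to 12, 18 and 24 gives 0.245, 0.250 and 0.252.

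| b (points) | Rate if counted | Looks at 6, 12, 18, 24 | Looks at 10, 20 |
|---|---|---|---|
| 0 (as written) | 15% | 25% | 6% |
| 1 | 16% | 28% | 7.5% |
| 2 | 17% | 31% | 9% |
| 5 | 20% | 41% | 16% |
| 10 | 25% | 58% | 31% |

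With q = 20% and looks at 6, 12, 18 and 24, the halt probability is 41% as written, against 48%, 58% or 73% for b = 2, 5 or 10 points.

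**The case against.** The strongest reply is that the sections serve different purposes. Section 11.2 is a tolerability endpoint for the first two cycles of a combination regimen. Section 12.5 triggers a review of single-agent Pola, in a phase without carboplatin, ifosfamide or etoposide. Section 12.5 is stricter in places, since a Grade 4 non-hematologic event generally counts however quickly it resolves. This stands: the difference is unexplained, but it is not a direct contradiction.

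Some stronger readings are tempting, and the documents do not support them.

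- A reader might infer that bleeding drops out of the 33% rule. It does not. Only the thrombocytopenia event is exempt, and hemorrhage is not among the exceptions.
- A reader might blame the exception for the loss of Grade 3 thrombocytopenia with bleeding. That follows from a definition that counts no Grade 3 event except neuropathy.
- A reader might take Section 12.5 as the only safeguard after transplant. Section 12.4 also monitors non-relapse deaths in the first 100 days after ASCT. Table 7.1 has dose-management steps for Grade 3–4 hematologic toxicity. Table 14.6 requires expedited SAE reports regardless of relationship. A serious bleed would be seen even where it is not counted.
- A reader might add that marrow reserve is lower in this phase. The documents do not say so, and the point does not need it.

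The size is also open to challenge. Nothing in the documents supports 5 or 10 points of otherwise uncounted patients, and Table 6.1 lists neither hemorrhage nor thrombocytopenia among the expected serious reactions in 635 exposed patients. This stands too, and is why the table in the working starts at 1 point and shows two look schedules.

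**Conclusion.** The point holds in a narrow form. As written, a related Grade 4 thrombocytopenia of 21 days or less, with clinically significant bleeding of Grade 3 or lower, is outside the post-transplant severe-toxicity count, although Section 11.2 calls it unacceptable during salvage. This rests on the text alone.

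The direction of the effect is certain for any patient with no other counted toxicity. The size is not known. Under the assumed rates and looks it runs from about 1.5 percentage points of halt probability (1 point uncounted, looks at 10 and 20) to 33 points (10 points uncounted, looks at 6, 12, 18 and 24). The low end is modest. At the first possible look, where 2 of 6 halts accrual, one such patient can decide the result, though at that sample size the same is true of any borderline event. The primary efficacy design is not affected. This is a small correction to a safety rule that is worth making.

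**What to change.** Reconcile the exceptions in Section 12.5 with Section 11.2, so that the 21-day exemption does not apply to thrombocytopenia with clinically significant bleeding. Do the same for the 10-day laboratory exception where it covers platelet counts. If the difference is intended, state the reason in Section 12.5.

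Separately, state whether Grade 3 thrombocytopenia with clinically significant bleeding should count after transplant. That is a design choice for the sponsor, because the definition otherwise counts only neuropathy at Grade 3.

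The cost is a few words in one section. Section 14.5 already records the highest grade of each toxicity per cycle and all SAEs, so no new adverse-event form is needed, although the link between a low platelet count and a bleed has to be made when events are classified. The downside is that accrual may be halted for DSMC review more often. A trigger leads to review and possible resumption, not to automatic termination.

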- 6) If there are 2 patients with unacceptable toxicities when 7 or 8 patients are treated, accrual to this dose level will be on hold if there are still any patients at risk. If the rate of unacceptable toxicity is ≥33% (i.e., 2 out of ≤6, 3/7, or 3/8 evaluable), the current dose level will be considered intolerable (and the dose de-escalated if at dose level 1); if the rate of unacceptable toxicity is <33% (i.e., 2/7 or 2/8 evaluable), the dose level will be considered tolerable.
- 7) Any time 3+ patients with unacceptable toxicities occur, the current dose level will be considered intolerable (and dose de-escalated if at dose level 1).

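### Section 12.5 ties its 33% toxicity limit for post-HCT Pola to 6-monthly reviews from 6 patients on, so even 3 events in the first 6 patients trigger no numeric halt until the next review

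*Combined protocol and SAP*

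**What the plan says.** Section 12.5 defines severe toxicity in consolidation as Grade 3 neuropathy that does not improve within a week, most Grade 4 events, and any Grade 5 event, at least possibly attributed to Pola or PolaR-ICE. The DSMC looks at toxicity every 6 months. The numeric rule "will start when there are at least 6 patients on the study who received post-HCT Pola". It reads: "If during such review, the proportion of patients having any of the severe toxicities is 33% or higher, the study accrual will be halted". A halt leads to a full review by the study team, then the DSMC, and "The study team may propose to modify the study if deemed necessary". Accrual resumes only with DSMC approval. No operating characteristics are given.

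The plan's other numeric rules are not tied to a review date:

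- Section 12.4, stem cell collection: "the rule will be triggered if at least 3/5, 4/10, 6/20, 8/30, or 10/40 patients fail to mobilize adequate CD34 cells within 2 attempts".
- Section 12.4, non-relapse death: "A second case of such death within 100 days following ASCT will trigger a stopping rule".
- Section 12.1.1, lead-in (salvage cycles 1-2 only): "If there are 2 patients with unacceptable toxicities when ≤6 patients are treated, the current dose level will be considered intolerable". With more patients, "if the rate of unacceptable toxicity is <33% (i.e., 2/7 or 2/8 evaluable), the dose level will be considered tolerable".

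Section 16.3 makes the PMT responsible for ongoing safety monitoring and for carrying out the stopping rules.

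**The concern.** Two features of 12.5 combine. No limit is in force before the sixth patient starts Pola, and from then on the limit is tested on calendar dates. A cluster of early events well above 33% therefore has no numeric consequence when it is reported.

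No other numeric rule fills the gap. Section 12.4 counts collection failures and non-relapse deaths within 100 days of ASCT, and the lead-in counts events in the first two salvage cycles. The lead-in therefore says nothing about Pola given after two or three PolaR-ICE cycles and a transplant. The background section itself describes neuropathy as the toxicity that limits Pola.

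What is at stake is the date of the full review, since that is where a change to consolidation would be proposed. Until then enrolment continues, and more patients start Pola under an unchanged plan.

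**Working it through.** Section 12.5 states no error rate, so there is no figure of its own to reproduce. As a check on the nearest comparator, the 12.4 collection rule has a Beta(0.15, 0.85) prior and acts when the posterior probability of a failure rate above 15% reaches 90%. That probability is 0.981 for 3/5 and 0.870 for 2/5, so 3/5 is correctly the first trigger at n = 5.

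**Inputs from the documents.** 40 evaluable patients and 24 months of accrual (12.3); 6-monthly reviews, a start at 6 patients and a 33% limit (12.5); 3-4 consolidation cycles of 21 days, that is 63 or 84 days, mean 73.5 (5.7); AE forms due within 10 days (13.3); 50% reaching ASCT in the historical R-ICE/R-DHAP trial (2.1.1).

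**Assumptions.** The same 50% reach Pola here. True severe-toxicity rates are 10/15/20/33/40%. Enrolment is even, the first Pola start is on day 150, events occur at a constant hazard over 73.5 days, and the review calendar has a random phase.

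**Step 1: the limit by number treated.** The smallest count reaching 33% is 2 at n = 6 (2/6 = 33.3%), 3 at n = 7-9 (3/9 = 33.3%) and 4 at n = 10-12. Three early events stay at or above the limit up to n = 9 and fall below it at n = 10 (3/10 = 30%).

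**Step 2: the timing.** Starts: 40 × 0.5 = 20 in 730 days, one every 36.5 days. Patient 6 starts 5 × 36.5 = 182.5 days after patient 1. Suppose patients 1-3 all have an event. Patient 3 starts on day 73, so that report arrives by day 73 + 73.5 + 10 = 156.5. Three of three events are then known at least 26 days before any limit exists, and the next review may be up to 6 months after that.

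**Step 3: how often 3 of the first 6 occurs.** P(X ≥ 3) = 1 − [(1−p)^6 + 6p(1−p)^5 + 15p²(1−p)^4]. At p = 0.33: 1 − (0.0905 + 0.2673 + 0.3292) = 0.313. At 10/15/20/33/40% the results are 1.6/4.7/9.9/31.3/45.6%.

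**Step 4: whole-trial chance of a halt** (simulation; the current rule halts at a review if n ≥ 6 and events ≥ 0.33n):

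| True rate | 10% | 15% | 20% | 33% | 40% |
|---|---|---|---|---|---|
| Current rule | 4% | 10% | 22% | 65% | 84% |
| Plus third event in first 6, at once | 4% | 11% | 23% | 65% | 84% |
| Plus second event in first 6, at once | 12% | 24% | 38% | 75% | 89% |

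To three decimals, the first two rows are 0.036 and 0.039 at 10%, 0.104 and 0.110 at 15%, and 0.222 and 0.229 at 20%. Each difference is under 1 percentage point.

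**Step 5: the delay.** A re-run with 100,000 trials per rate looked at trials with 3 events among the first 6 that the current rule eventually halts. At 33% the halt comes a median of 3.0 months after the third report (quartiles 1.4 and 4.7). At 10/15/20% the medians are 2.3/2.5/2.7 months. The current rule never halts 15/11/8/2/1% of these clusters at 10/15/20/33/40%. At 33% a median of 2 further patients start Pola during the delay, and about 3.0 × 40/24 = 5 enrol.

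**Sensitivity.** The re-run varied the share reaching consolidation (40-80%), the event window (63 or 84 days), the reporting lag (10 or 31 days) and the first start (day 120 or 180). The median delay is 2.7-3.2 months at 33% and 2.3-3.1 months at 20%. The added halts reach about 2 to 2.5 points if 80% reach consolidation (14.8% to 17.3% at a true rate of 20%; 63.6% to 65.7% at 33%).

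**The case against.** The strongest reply is that oversight does not wait for the number. Section 16.3 gives the PMT ongoing monitoring and has it consider whether further enrolment is appropriate. Section 14.6 expedites serious events, within 24 hours from non-COH sites. Section 7.1 withholds, reduces or stops Pola in the affected patient. A minimum denominator is also a legitimate choice, since without one 1/1, 1/2 and 1/3 would all meet 33%. All of this stands. What remains is that 16.3 has the PMT carry out the stopping rules, and before patient 6 there is none for this phase. Afterwards 12.5 places the test at the DSMC review.

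Three stronger readings are tempting, and the documents do not support them:

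- *A toxic consolidation would go undetected.* At a true rate of 33%, only about 2% of three-event clusters are never halted under the base assumptions.
- *Two events in the first 6 must halt at once, as in the lead-in.* The lead-in tests a new combination, and it accepts 2/7 and 2/8. Section 12.4 does not act on 2/5. A two-event trigger adds about 8, 14 and 16 points of halts at tolerable rates of 10, 15 and 20% (12 − 4, 24 − 10, 38 − 22), against 10 points at 33%. It could also halt at 2/7 or 2/8, below the plan's own limit.
- *Patients who start Pola during the delay would have been spared.* A halt stops accrual and not dosing. The earliest Pola dose is 2 × 21 + 30 = 72 days after starting treatment, so many of those patients are already enrolled. They gain only if the review changes the plan.

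**Conclusion.** The point holds as a matter of timing. The text of 12.5 alone shows that 3 severe toxicities among the first 6 patients have no numeric consequence until a scheduled review. The size is modest: a median of about 3 months at a true rate of 33%, and about 2 to 3 months at 10-20%. These figures rest on assumed toxicity rates, patient flow and review timing, because the documents give none of them for this regimen. Detection over the whole trial hardly changes. At true rates of 10-20%, below the limit, not halting is usually the intended result. This is an inexpensive improvement to a safety rule and does not show that the trial is unmonitored.

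**What to change.** Add to Section 12.5:

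> The PMT applies this rule as events are reported, from the first patient who receives post-HCT Pola: a third patient with a severe toxicity among the first 6 treated halts accrual pending DSMC review, even if a seventh patient has started. The 33% limit continues to apply at each DSMC review from 6 patients.

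Add one line of operating characteristics with its assumptions: chance of a halt of about 4/11/23/65/84% at true rates of 10/15/20/33/40%. The clause on a seventh patient is needed because the third event can be reported after that patient has started.

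The cost is two sentences and one line. No staff or data are added, since the PMT already carries out the stopping rules and the AE forms already arrive within 10 days. The price is under 1 percentage point more reversible pauses under the base assumptions (up to about 2.5 if 80% reach consolidation). Two-event clusters stay as they are now. A limit of 2 among the first 6 is a stricter option if the sponsor accepts halts of 12/24/38% at true rates of 10/15/20%.
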